9.4.2.1 Chemical Name and Formula of Elenbecestat (E2609)

- Test drug code: E2609
- Generic name: Elenbecestat (pINN)
- Chemical name: International Union of Pure and Applied Chemistry
- *N*-{3-[(4*a*S,5*R*,7*a*S)-2-Amino-5-methyl-4*a*,5-dihydro-4*H*furo[3,4-*d*][1,3]thiazin-7*a*(7*H*)-yl]-4-fluorophenyl}-5-(difluoromethyl)pyrazine-2-carboxamide
- Molecular formula: C₁₉H₁₈F₃N₅O₂S
- Relative molecular mass: 437.44

9.4.2.2 Comparator Drug

Not applicable.

9.4.2.3 Labeling for Study Drug

Elenbecestat (E2609) will be labeled in accordance with text that is in full regulatory compliance with each participating country and is translated into the required language(s) for each of those countries. The following information may be included but is not limited to:

- Protocol number
- For clinical study use only
- Name and address of the sponsor
- Chemical name/drug identifier (ID)
- Lot number/batch number
- Storage conditions, expiration date if necessary

9.4.2.4 Storage Conditions

Study drug will be stored in accordance with the labeled storage conditions. Temperature monitoring is required at the storage location to ensure that the study drug is maintained within an established temperature range. The investigator or designee (or if regionally required, the head of the medical institution) is responsible for ensuring that the temperature is monitored throughout the total duration of the study and that records are maintained; the temperature should be monitored continuously by using either an in-house validated data acquisition system, a mechanical recording device, such as a calibrated chart recorder, or by manual means, such that minimum and maximum thermometric values over a specific time period can be recorded and retrieved as required.

9.4.3 Method of Assigning Subjects to Treatment Groups

Subjects will be assigned to treatments based on a computer-generated randomization scheme. The randomization scheme and identification for each subject will be included in the final clinical study report for this study. The doses and number of treatment groups are described in [Section 9.4.1](#). (revised per Amendments 01 and 05)

Randomization will be performed centrally by an IxRS. The IxRS or clinical supply vendor will generate the randomized blister card identification numbers. At enrollment, the investigator or designee will call the IxRS to register the subject information. At randomization (Visit 3), the IxRS will assign each subject a unique randomization number.

9.4.4 Selection of Doses in the Study

It is not known how the level of CSF or brain A β reduction is related to clinical efficacy. Therefore, in this study, initial doses will be selected such that at steady state, they will result in 25%, 50%, and 75% reduction in CSF A β levels from baseline to cover a broad range of PD effects. (revised per Amendment 06)

In Study 007, the relative bioavailability of a tablet formulation of elenbecestat (E2609) in the fed and the fasted states compared with the capsule formulation in the fasted state (used in Studies 001 and 002) was investigated. It was found that when the tablet form of elenbecestat (E2609) (50 mg) was administered with food, the exposure (ie, AUC) of the parent drug elenbecestat was higher, with lower maximum observed concentrations and reduced exposure to the metabolites, compared with either formulation in the fasted state.

Based on the PK/PD modeling using data from healthy volunteer Studies 001, 002, and 007, doses of 5, 15, and 50 mg QD administered as the tablet formulation with food in this study should achieve CSF A β reduction from baseline of approximately 25%, 50%, and 75% at steady state, respectively (Table 3).

Table 3 Predicted Steady State Plasma PK Parameters and CSF Amyloid β Reduction From Baseline

| Elenbecestat (E2609) Tablet Daily Dose (mg) With Food | Plasma Elenbecestat (E2609) | | | % Reduction CSF BACE1 Activity | % Reduction CSF A β (1-x) |
|---|--------------------------------|-------------------------------|---------------------------------------|-----------------------------------|------------------------------------|
| | C _{max,ss} (ng/mL) | C _{ss,av} (ng/mL) | AUC _{(0-24h)ss} (ng·h/mL) | | |
| 5 | 6.2 | 3.3 | 80.3 | 16.2 | 33 |
| 15 | 18.6 | 10 | 240.9 | 36.6 | 56 |
| 50 | 62.1 | 33.5 | 803.0 | 65.7 | 79 |

A β (1-x) = amyloid beta monomer from amino acid 1 to x, AUC_{(0-24h)ss} = area under the concentration x time curve at steady state from time zero to 24 hours, BACE1 = beta-amyloid converting enzyme, CSF = cerebrospinal fluid, C_{ss,av} = average steady-state concentration, C_{max,ss} = maximum plasma concentration at steady state, PK = pharmacokinetics.

The PK/PD modeling described above, which was conducted using data obtained from healthy volunteers, has also been supported by modeling of data from subjects with an underlying AD pathology (Study 101). Furthermore, external data with another BACE1 inhibitor (MK-8931) showed a similar PD effect in AD patients as in healthy volunteers (Forman, et al., 2013). Therefore we are confident that the modeling of elenbecestat (E2609) effects in healthy subjects will be applicable for both MCI/Prodromal and mild to moderate AD dementia patients. (revised per Amendment 01)

The exposure of the highest dose in this study (50 mg QD tablet administered with food) is less than that of the 100 mg QD dose (capsule administered fasted) in Study 002.

The 100 mg QD dose administered for 14 days in Study 002 was well tolerated with no clinically significant changes in laboratory parameters, vital signs, or ECG parameters. On Day 15, for the 100 mg QD cohort in Study 002, there was a reduction of CD4 lymphocyte counts compared with placebo (CD4 lymphocyte counts on elenbecestat (E2609) decreased by 3.1% from baseline, whereas the placebo control showed an increase of 8.7%), but this decrease was less than that observed at doses of 200 mg (22.9% decrease) or 400 mg (17.3% decrease). No subject had infections or drug rash while receiving elenbecestat (E2609) 100 mg QD or at lower doses in Study 002, whereas at 200 and 400 mg QD, 4 subjects had symptomatic orolabial HSV1 relapses and 2 subjects at the highest dose had drug rash. The highest dose for Study 202 of 50 mg QD (tablet administered with food) is therefore expected to have a similar or better safety profile compared with the 100 mg QD capsule (administered fasted) in Study 002. Specific exclusion criteria, blinded and unblinded safety monitoring procedures, and safety criteria for discontinuation from study drug are included in this study in order to mitigate any immunology-related risk with elenbecestat (E2609), particularly in light of the progression from 14 days of dosing (Study 002) to 18 months of dosing in this study.

Interim analyses of the elenbecestat (E2609) plasma PK for all subjects and the elenbecestat (E2609) CSF PK and PD profiles will be performed on baseline data and samples collected after at least 4 weeks of treatment. These interim analyses, as well as analyses of safety data, will be performed on an ongoing basis. Refer [Section 9.7.3](#) for more detail. The median and mean percentage change from baseline in CSF A β (1-x) measured after 4 weeks of treatment for each dose of elenbecestat (E2609) and its 90% confidence interval for the median will be derived. In addition, exploratory PK/PD modeling will be conducted. This PK/PD modeling will use the observed PK and PD data and will relate the average steady state plasma concentration of elenbecestat (E2609) to steady state CSF A β (1-x) percentage reduction from baseline after at least 4 weeks of dosing. (revised per Amendments 01, 02, 03, 04, and 05)

Unblinded interim analyses have indicated elenbecestat (E2609) 50 mg per day produced relatively high levels of CSF A β reduction (greater than 50%) with an acceptable safety profile. As a result, elenbecestat (E2609) 50 mg has been selected as the dose for Phase 3 development. To gain a more comprehensive safety and tolerability profile of elenbecestat (E2609) 50 mg, subjects randomized to elenbecestat (E2609) 5 and 15 mg will be re-assigned to elenbecestat (E2609) 50 mg for the remaining of the 18-month treatment period with the provision that they will have at least 12 weeks of treatment remaining in the Randomization Phase. (revised per Amendment 06)

9.4.5 Selection and Timing of Dose for Each Subject

Elenbecestat (E2609) is administered orally, QD, with food. Study treatment will begin on Day 1 following randomization and will continue for approximately 78 weeks.

9.4.6 Blinding

Elenbecestat (E2609) and placebo will be administered as tablets of identical appearance during the Core Study.

During the Randomization Phase and Follow-Up Phase in the Core Study, subjects, caregivers/informants, and all clinical site personnel involved with the conduct and interpretation of the study, including investigators will be blinded to the treatment codes (double-blind). In order to make decisions about the remainder of the study as well as the full elenbecestat (E2609) clinical development program, the sponsor will unblind safety, PK, and PD data on an ongoing basis and perform interim analyses of these data. (revised per Amendment 03)

Every effort should be made to keep the site staff responsible for reviewing laboratory reports and assessing AEs separate from the site staff responsible for the efficacy assessments, particularly for the CDR (ie, those who are trained and certified to perform the various cognitive assessments that are undertaken in this study). Furthermore, at the site, the notes and reports relating to safety assessments must be kept separate from the notes and reports relating to efficacy, particularly for the CDR. (revised per Amendment 01)

Randomization data will be kept strictly confidential, filed securely by an appropriate group with the sponsor or CRO and accessible only to authorized persons (eg, Eisai Global Safety) until the time of unblinding, per the standard operating procedure.

The PK/PD interim analyses will take place throughout the study as per Amendment 03 and will be conducted by an independent PK/PD scientist at the sponsor. Any additional changes to dose required for this study will be reflected in a further amendment to the protocol and the Statistical Analysis Plan will detail how data will be handled in the primary analysis. (revised per Amendments 02 and 04)

In the event that emergency conditions require knowledge of the study treatment given, the blind may be broken via the code breaker facility within the IxRS. Emergency procedures for revealing drug codes are given in [Section 9.5.4.5](#). If possible, before breaking the blind, the investigator should consult with the sponsor to ascertain the necessity of breaking the code.

At the conclusion of the study, all unused drug supplies are to be returned to the Eisai approved contract packaging vendor.

9.4.7 Prior and Concomitant Therapy

Medication (including over-the-counter medications) or therapy administered to the subject before the study (within 6 months of randomization) and during the study (starting at the date of informed consent) will be recorded on the Prior & Concomitant Medication eCRF or Non-Pharmacological Procedures eCRF. The investigator will record on the Adverse Event eCRF any AE for which the concomitant medication/therapy was administered. If the concomitant medication/therapy is being administered for a medical condition present at the time of entry into the study, the investigator will record the medical condition on the Medical History and Current Medical Condition eCRF.

Listings of prohibited and permitted drugs during the Core Study and OLE Phase are provided in [Appendix 2](#). (revised per Amendment 07) Prohibited medications are presented in [Listing 1](#) through [Listing 5](#). Medications that are permitted with restrictions are listed in [Listing 6](#) through [Listing 8](#). (revised per Amendment 04)

The types of agents listed below are not permitted before randomization unless discontinued according to the specific timeframes as shown below; these types of agents are not permitted during the Core Study or OLE Phase until after the last treatment visit: (revised per Amendments 04 and 07)

- Drugs which may cause QTc prolongation are not permitted for a period of 5 half-lives or 14 days (whichever is longer) before randomization
- Strong CYP3A4 inhibitors are not permitted for a period of 5 half-lives or 14 days (whichever is longer) before randomization
- Live vaccines are not permitted within 3 months before randomization. This does not apply to non-live/inactivated vaccines

- Ig therapy and biologic drugs are not permitted within 6 months before randomization
- Systemic or ocular immunosuppressive or immunomodulatory drugs are not permitted for a period of 5 half-lives or 60 days (whichever is longer) before randomization. However, during the treatment period of the study, short term (not more than 14 days) use of steroids up to the equivalent of prednisolone 40 mg once daily is permitted after discussion with the Medical Monitor. Dosing with study drug should be suspended from the time steroid treatment is started. Complete blood count and lymphocyte subsets should be determined prior to starting steroid treatment and continue to be monitored weekly. Study drug may be resumed after discussion with the Medical Monitor when the following conditions are met: (1) treatment with steroids has been completed for at least 1 week; (2) absolute lymphocytes not <LLN; (revised per Amendments 07) (3) no lymphocyte subsets are below the discontinuation threshold (for Core Study only); (4) the investigator considers that the medical condition which required treatment with steroids has improved or resolved. Weekly testing of lymphocyte subset counts (for Core Study only) and CBC with differentials is required for 4 weeks following resumption of study drug administration. (revised per Amendment 04)
- (revised per Amendment 06)

Subjects who initiate treatment with an AChEI or memantine during the study, or who change their dose of AChEI or memantine while on study, will be allowed to continue in the study, but their clinical efficacy data will be censored from the time of drug initiation for any efficacy analyses. (revised per Amendment 05)

Subjects taking all other non-prohibited concomitant medications must meet the following requirements:

- Must be on stable dose for at least 4 weeks before randomization, except for medications that are administered as short courses of treatment or which are to be used intermittently as needed. Subjects who are on anticoagulants may have a variable dose but should have stable anticoagulation control for at least 4 weeks before randomization. They may be required to stop their anticoagulant medication prior to CSF collection and then restart this medication after the LP procedure, as per local guidelines. (revised per Amendment 04)
- Medications that are used as needed, rather than on a stable daily basis, and which are central nervous system (CNS) active and may affect cognitive function, are not permitted during a period of 72 hours before cognitive testing

Subjects who initiate treatment with or have dose adjustment of drugs not intended for treatment of cognitive impairment during the study may continue in the study if in the opinion of the investigator this will not interfere with study procedures or subject safety, and are not prohibited above. (revised per Amendment 05)

Antiplatelet therapy: (revised per Amendment 04)

- For subjects who consent to CSF sample collection: Either aspirin or clopidogrel (or any other antiplatelet drug which is not aspirin) are permitted in all subjects. Aspirin and clopidogrel (or any other antiplatelet drug which is not aspirin) in combination are also

permitted but subjects who are on such a combination of antiplatelet drugs may be required to stop 1 or more of these antiplatelet drugs before the LP procedure and restart after the LP as per local guidelines.

- For subjects who do not consent to CSF sample collection: Aspirin and clopidogrel, individually or in combination, are permitted.

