In the MAD study, AEs of interest included relapse of orolabial herpes, viral respiratory tract infection, drug rash, and abnormal dreams. More details are available in the Investigator's Brochure. In summary, elenbecestat (E2609) administered at doses of 200 and 400 mg was associated with reductions in CD4 (T helper cells), CD8 (cytotoxic T cells), and CD19 (B cells) counts at Day 8. These reductions were more clearly evident by Day 15, consistent with a treatment by time interaction in the statistical analysis. There was evidence that the lower doses of 50 to 100 mg also caused some reduction in CD4 lymphocyte counts by Day 15. Doses above 100 mg appeared to be associated with greater reductions in CD4 and CD8 lymphocyte counts, which occurred earlier in the treatment period compared with the effects of 25 to 100 mg doses. These effects on lymphocyte counts gradually resolved from Day 20 to Day 35, which were 6 and 21 days, respectively, after administration of the last dose of elenbecestat (E2609) on Day 14. Reductions in CD4 and CD8 lymphocyte counts at doses of 200 and 400 mg to a level close to or less than the lower limit of normal (LLN) could be associated with increased risk of developing relapse of orolabial herpes or other infections.

In Study 003, a drug-drug interaction study, PK results showed that itraconazole (a potent inhibitor of cytochrome P450 [CYP3A4] and carboxyesterase-2 [CES2]) increased by approximately 70% the area under the concentration \times time curve (AUC) of elenbecestat (E2609). Consequently, strong inhibitors of CYP3A4 will be prohibited in this study.

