9 INVESTIGATIONAL PLAN

9.1 Overall Study Design and Plan

This study is a multicenter, placebo-controlled, double-blind, parallel-group, randomized, dose-finding study with an OLE Phase of up to 27 months in subjects with MCI/Prodromal AD or mild to moderate AD. (revised per Amendments 01 and 07)

A common set of inclusion criteria, consistent with the NIA-AA clinical research criteria for MCI due to AD or mild to moderate AD, will be required for all subjects. In addition, the MCI due to AD population will also be consistent with the research criterion for “Prodromal AD” in that episodic memory will be impaired on a list learning task (ISLT). As the non-demented subjects will be consistent with criteria for both MCI due to AD and Prodromal AD they will be identified as MCI/Prodromal subjects in this protocol. The diagnosis of MCI/Prodromal AD or mild to moderate AD will be based on both clinical and biological (ie, confirmation of amyloid load in the brain) criteria. (revised per Amendment 01)

The study consists of 3 phases: Prerandomization, Randomization, and OLE. The Prerandomization and Randomization Phases are referred to as the Core Study throughout the protocol. (revised per Amendment 07).

The Prerandomization Phase (up to 60 days, plus an additional window of up to 30 days if required [revised per Amendment 02]) will consist of a Screening Visit and a Baseline Visit. Screening assessments will be organized into 4 tiers; see [Section 9.5.2.2](#), [Table 6](#), and [Figure 2](#).

All screening assessments must be completed, and eligibility to continue to the Baseline Period confirmed, before any baseline assessments commence. Following successful completion of the Prerandomization Phase, eligible subjects will be randomized and will enter the Randomization Phase, which will consist of 2 periods: Treatment (78 weeks) and Follow-Up (post last dose; 12 weeks).

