9.1.2 Randomization Phase

Subjects who complete the Baseline Visit assessments, and are eligible based on the inclusion and exclusion criteria (see [Section 9.3.1](#) and [Section 9.3.2](#)), will begin the Randomization Phase no more than 10 days after completion of the Baseline Visit assessments and confirmation of the eligibility of the subject based on the results of all the Baseline Visit assessments (revised per Amendment 02).

The Randomization Phase will consist of a Treatment Period of 78 weeks duration and a Follow-up Period of 12 weeks after the last dose of study drug.

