9.2.5 Clinical Risks and Mitigation Strategy

A number of safety aspects have been built into the design of this study in light of the preclinical and clinical safety data with elenbecestat (E2609), and to mitigate clinical risk in the progression from 14 days of dosing in the MAD study to 18 months of Core Study treatment and 24 months of OLE Phase treatment in this Phase 2 study. (revised per Amendment 07) These safety aspects include the following:

- Immunology-related and infection-related exclusion criteria for both the Core Study and the OLE Phase (revised per Amendment 07)
- Review of unblinded safety data by an independent DSMB at regular intervals
- Safety criteria for study drug discontinuation based on CD4 (T helper cells), CD8 (cytotoxic T cells), CD19 (B cell) during the Core Study and absolute lymphocytes during the OLE Phase (revised per Amendment 07)
- Safety criteria for study drug discontinuation during the Core Study and OLE Phase based on skin rash, reoccurrence of herpes virus infections including any oral herpes, genital herpes or shingles, other infections, MRI changes, ECGs, and pregnancy. (revised per Amendment 07)

In addition to the features above, other safety aspects of this study designed to mitigate clinical risk include the following:

- Blinded safety data will be monitored by Eisai at regular intervals during the course of the study
- Routine safety assessments will include the monitoring and recording of all AEs and SAEs, monitoring of hematology, blood chemistry, and urinalysis, measurement of vital signs, regular ECGs, physical and neurological examinations, and dermatological assessments at regular intervals. (revised per Amendment 07) AEs that might indicate signals of possible drug abuse potential will require a detailed follow-up. Subjects reporting AEs relating to abnormal dreams, nightmares, or sleep terror will be questioned on the frequency and impact of these events. To assess potential immunomodulatory effects, peripheral blood mononuclear cells (PBMCs) will be collected at baseline, during treatment, and posttreatment.

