- h: Only if clinically significant abnormalities are found at Visit 33 and the investigator considers it necessary to repeat at Visit 34.
- i: Measurements of body temperature and sitting blood pressure and sitting heart rate will be obtained.
- j: Result from Visit 20 will also serve as Visit 21 result if Visit 21 occurs within 10 days from Visit 20. If Visit 21 occurs more than 10 days after Visit 20, the assessment must be repeated at Visit 21.
- k: Examples of neurological signs that may indicate new central nervous system pathology that may need further investigation include (but not limited to) visual disturbance, dysarthria, dysphasia, muscle strength, limb weakness, hyperflexia, paraparesis, micturition difficulty or urgency or incontinence, ataxia, neuropsychiatric or cognitive decline in excess of expectations based on the subject’s recent history. The Brief Smell Identification Test (Sensonics Inc.) will be administered at the same visits and serves as part of the neurologic examination.
- l: Please refer to Section 9.4.7 which describes prohibited and permitted medications in the study.
- m: Result from Visit 20 will also serve as Visit 21 result if Visit 21 occurs on the same day as Visit 20. If Visit 21 occurs more than 1 days after Visit 20, the assessment must be repeated at Visit 21.
- n: Single 12-lead standard ECGs will be recorded. If the QTcF is greater than 450 ms, perform 2 more 12-lead standard ECGs 1 minute apart and take the mean of the 3 QTcF values.
- o: Reports of the lymphocyte subset analyses will be sent to the Sponsor only. Lymphocyte subsets will include but are not limited to the following cell surface marker assessments: CD4 [T helper cells], CD8 [cytotoxic T cells], CD19 [B cells], CD16/CD56 [NK cells] and CD14 [macrophages] and absolute lymphocytes. Regulatory T cells will also be measured. Viability staining may also be employed.
- p: PD blood samples should be collected at fasting or at least 2 hours after the most recent meal and, as far as is feasible, samples should be taken at the same time of day. All PD blood samples should be collected predose.
- q: If dipstick urinalysis performed at site is abnormal, a urine sample will be sent to the central laboratory for full urinalysis.

-

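### Medication washouts in Section 9.4.7 count back only from randomization, and Appendix 6 has no OLE entry exclusion for a recent live vaccine or prohibited-medication use

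*Protocol*

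**What the plan says.** Section 9.4.7 covers both phases: "these types of agents are not permitted during the Core Study or OLE Phase until after the last treatment visit". Before dosing, the agents are "not permitted before randomization unless discontinued according to the specific timeframes as shown below", and the timeframes that follow all refer to randomization. For example, "Live vaccines are not permitted within 3 months before randomization"; immunoglobulin therapy and biologics have a 6-month interval, and immunosuppressive or immunomodulatory drugs 5 half-lives or 60 days, whichever is longer. Listings 1 to 5 in Appendix 2 use the same anchor.

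Section 9.3 makes OLE eligibility depend on the criteria in Appendix 6. For concomitant medications, Table 14 (footnote l) sends sites back to the main text: "Please refer to Section 9.4.7 which describes prohibited and permitted medications in the study".

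Section 9.1 states that "The Prerandomization and Randomization Phases are referred to as the Core Study throughout the protocol", and Section 9.1.2 describes the Randomization Phase as "a Treatment Period of 78 weeks duration and a Follow-up Period of 12 weeks after the last dose of study drug". Visit 21 may fall on the day of Visit 20 or within 4 weeks of it; a longer delay involves the Medical Monitor.

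Section 9.2.5 lists among its safety measures "Immunology-related and infection-related exclusion criteria for both the Core Study and the OLE Phase".

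**The concern.** Before their first Core dose, subjects had to be 3 months clear of live vaccines and 6 months clear of immunoglobulin and biologics. At Visit 21 former placebo subjects take active drug for the first time, and the others restart after at least 12 weeks off. No written rule asks for either interval at that point. A site checking medications at Visit 21 is sent to Section 9.4.7 and finds no interval that ends at that visit.

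The washouts exist because of the drug's possible effect on lymphocytes. Section 7.2 reports for the multiple-dose study that "the lower doses of 50 to 100 mg also caused some reduction in CD4 lymphocyte counts by Day 15", and the OLE dose is 50 mg. What is at stake is consistency of a safety precaution at entry to the second dosing phase, not any estimate or test.

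**Working it through.** The plan gives no figure to reproduce. The check is a comparison of criteria followed by date arithmetic.

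**Core exclusions (Section 9.3.2) against OLE exclusions (Appendix 6)**

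- Core 14 to 18 (immunodeficiency, viral hepatitis, tuberculosis, ophthalmic shingles, ocular herpes simplex) correspond to OLE 4d to 4h.
- Core 20 (active infection within 4 weeks) corresponds to OLE 2, re-anchored to Visit 21.
- Core 21 (chronic inflammatory disease) corresponds to OLE 4i.
- Core 22 (CD4, CD8, CD19 counts) is replaced by OLE 3, absolute lymphocyte count.
- Core 23 (IgG, IgA, IgM below normal) has no laboratory counterpart.
- Core 19 (live vaccine) has no counterpart.
- Core 37 (violation of the medication restrictions) has no counterpart.

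**Length of the off-drug interval**

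Inputs: Visit 18 at Day 547 and Visit 20 at Day 631 (Table 7); up to 4 weeks, 28 days, from Visit 20 to Visit 21 (Appendix 6). Assumptions: 3 months = 91 days, 6 months = 182 days; the ±3-day visit windows are ignored.

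- Same-day entry: 631 − 547 = 84 days.
- Latest entry without Medical Monitor involvement: 84 + 28 = 112 days.

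**Distance from the Core intervals**

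- Live vaccine, same-day entry: 91 > 84, so one given at any time in the gap is inside 3 months of Visit 21.
- Live vaccine, entry at 112 days: one given in the last 91 days is inside 3 months; 91/112 = 81% of the gap.
- Immunoglobulin or biologic: inside 6 months throughout, short by at least 182 − 84 = 98 days or 182 − 112 = 70 days.
- Given between Visits 20 and 21 only: a live vaccine is short by at least 91 − 28 = 63 days, an immunoglobulin or biologic by at least 182 − 28 = 154 days.

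**What the text does with such use**

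- Continuous reading: the last treatment visit for someone who goes on is the last OLE treatment visit, Visit 32. Use in Core follow-up or between Visits 20 and 21 breaches Section 9.4.7. With no counterpart to Core 37, the breach is a deviation and not a listed bar to entry.
- Per-phase reading: the Core ban ends after Visit 18 and the OLE ban starts at Visit 21. Use in the 84 to 112 days between is allowed.

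**Other guards**

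OLE 3 and 4i largely catch immunosuppressants. OLE 2 catches active infection. OLE 10 and 11 turn on the investigator's judgment of conditions and abnormal findings. None names a vaccine, immunoglobulin or a biologic. Listing 3 includes agents that need not be given for inflammatory disease, such as bevacizumab and ranibizumab.

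**Subjects**

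60 × 0.8 = 48 to 60 × 1.2 = 72 randomized; one quarter on placebo, 12 to 18. Only completers may enter the OLE. The documents give no frequency of use for any of these agents.

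**The case against.** The strongest reply is that the ban is continuous. The Listing 4 title describes one window, from 3 months before randomization until after the last treatment visit, with no phase boundary. The Core Study by definition includes the 12-week follow-up. On that natural reading a live vaccine before Visit 21 is already prohibited, and a subject who complies needs no second washout. This stands, and it narrows the point: what remains is that a breach has no stated consequence for entry.

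Section 9.4.7 also allows a subject who starts a drug not intended for cognitive impairment to stay in the study only if that drug is not prohibited. This withholds permission from someone starting a biologic, but it sets no interval before Visit 21, is not an OLE criterion, and fits a single vaccination poorly.

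Three stronger readings are tempting and are not supported:

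- A reader might infer that the live-vaccine rule is the only immune criterion lost in transfer and so an evident slip. Core 23 also lacks a laboratory counterpart, Core 22 was replaced, and other Core criteria were dropped; Appendix 6 is a shortened list.
- A reader might infer that the protocol freely permits these agents in the gap. That holds only on the per-phase reading.
- A reader might infer demonstrated harm. Section 9.4.4 reports a CD4 fall of 3.1% at 100 mg, against a rise of 8.7% on placebo, and no infections at 100 mg or below in the multiple-dose study; Section 7.1 describes the interim safety findings as favorable at all doses.

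**Conclusion.** The point holds as a modest gap in safety eligibility. On either reading of the ban, a live vaccine shortly before Visit 21, or an immunoglobulin or biologic given outside OLE 4i, is not by rule a bar to OLE entry. On the continuous reading it is a deviation; on the per-phase reading it is allowed for 84 to 112 days.

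The day counts show how far such use could fall short of the Core intervals. They do not measure risk or the number of people affected, which cannot exceed the completers among 48 to 72 randomized subjects. Sample size, error rates and the analyses are untouched. The conclusion rests on the body of Section 9.4.7 and on Appendix 6; the current synopsis text on concomitant therapy is not in the part available.

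**What to change.** - Add an OLE exclusion to Appendix 6: a live vaccine within 3 months before Visit 21, or any other agent prohibited by Section 9.4.7 within its stated washout before Visit 21.
- In Section 9.4.7, anchor the washouts to randomization and Visit 21, and keep the short-course steroid rule.
- State that the bans continue through Core follow-up until Visit 21 for any subject who may enter the OLE. Defining the last treatment visit by whether the subject later enters would not work prospectively, because entry may be decided at or after Visit 20.
- Bring the Listing 3 title into line with Section 9.4.7; it omits the on-study ban.

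The data are already collected: medications in the 12-week follow-up are recorded (Section 9.7.1.5), and Table 14 repeats the check when Visit 21 is not on the day of Visit 20. The cost is in entry. A few subjects may be delayed. A subject given immunoglobulin or a biologic during follow-up would be at least 70 days short even at the end of the 4-week window, and so would need Medical Monitor permission for late entry or would miss the OLE.
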